7.1.1. Olaratumab Premedications and Required Monitoring

The infusion rate of olaratumab should not exceed 25 mg/min. Infusion durations longer than 60 min are permitted in specific circumstances (that is, for patients with higher body weight for whom the upper limit of infusion rate is limited or in the setting of prior olaratumab Grade 1 or 2 infusion-related reaction [IRR]); the infusion duration must always be accurately recorded.

Premedicate patients prior to administration of olaratumab as below:

- On Days 1 and 8 of Cycle 1: **Mandatory** administration of a histamine H1 antagonist (for example, diphenhydramine) and dexamethasone prior to the start of the olaratumab infusion.
- For subsequent cycles, premedication with a histamine H1 antagonist (for example, diphenhydramine) is recommended prior to each dose of olaratumab.

Additional premedication(s) may be provided at the investigator's discretion. Premedication must be provided in the setting of a prior Grade 1 or 2 olaratumab IRR, as detailed in Section 7.8.1. All premedications administered must be adequately documented in the electronic case report form (eCRF).

Patients are required to be monitored for 1 hour after the olaratumab infusion in Cycles 1 and 2 for signs or symptoms of IRRs; see Section 7.8.1 for full description of required olaratumab monitoring period in Cycles 1 and 2. Patients should complete the required monitoring period prior to the start of the doxorubicin administration.

7.1.2. Doxorubicin Premedications and Dexrazoxane Administration

Given the emetogenic potential of doxorubicin, premedication with antiemetics per institutional guidelines is recommended. Additional premedication(s) may be provided at the investigator's discretion.

If antiemetic premedication is required prior to the doxorubicin infusion, this must be done after the completion of the olaratumab infusion (*not before the olaratumab infusion*). This premedication may be administered immediately following the end of observation period (if applicable) or after the completion of the olaratumab infusion.

Patients may receive dexrazoxane for the prevention of cardiotoxicity at the discretion of the investigator according to institutional protocol.

7.1.3. Ifosfamide Premedications and Mesna Administration

Mesna must be administered to all patients for the prevention of ifosfamide-induced hemorrhagic cystitis. Mesna should be administered at a minimum dose equal to 60% of the ifosfamide dose according to institutional guidelines. Note that as the dose of mesna administered is dependent on the dose of ifosfamide administered, any dose modifications to ifosfamide will require a corresponding dose modification to mesna in order to maintain the correct dosage (mesna dose = minimum 60% of ifosfamide dose).

Ifosfamide should be given with extensive hydration consisting of oral or IV fluid (≥ 2 L/m² per day IV) to prevent bladder toxicity or according to institutional guidelines.

Ifosfamide is associated with moderate emetic potential and antiemetics are recommended to prevent nausea or vomiting.

If ifosfamide premedication is required, it should be administered together with any doxorubicin premedications prior to doxorubicin administration.

7.2. Method of Treatment Assignment

Patients who meet all criteria for enrollment will be assigned to receive olaratumab in combination with doxorubicin, ifosfamide and mesna in this study. After the patient signs the ICF, the site will register the patient in the interactive web response system (IWRS), which is web-based and accessible 24 hours a day. The IWRS registration consists of assigning the patient a unique study identification number. Once the patient is registered through the IWRS, he/she is considered to be enrolled in the study.

7.2.1. Selection and Timing of Doses

A cycle is defined as an interval of 21 days. In Cycle 2 and beyond, up to 3 days delay of a cycle (that is, Day 1) or Day 8 will be permitted due to holidays, weekends, bad weather, or other unforeseen circumstances and will not count as a protocol deviation. In exceptional cases, longer delays may be allowed in later cycles following consultation with Lilly medical representative.

The actual dose of olaratumab to be administered will be determined by measuring the patient's weight in kilograms on Days 1 and 8 of each cycle. See also Section 7.5 for further details on olaratumab. The actual doses of doxorubicin, ifosfamide and mesna to be administered will be determined by calculating the patient's body surface area at the beginning of each cycle. If the patient's weight does not fluctuate by $\pm 10\%$ from the weight used to calculate prior doses, the olaratumab and doxorubicin, ifosfamide and mesna doses will not need to be recalculated, unless deemed clinically meaningful. A $\pm 5\%$ variance in the calculated total doses will be allowed for ease of dose administration.

Patients will continue treatment for a maximum of 6 cycles, or until there is documented disease progression, unacceptable toxicity, death, or other discontinuation criteria are met (Section 8). Patients who discontinue doxorubicin, ifosfamide and mesna treatment without evidence of disease progression will receive olaratumab as monotherapy until there is evidence of disease progression, death, intolerable toxicity, or other withdrawal criteria are met (Section 8). Patients who undergo surgical tumor resection following study treatment are not eligible to receive olaratumab as monotherapy.

		≤5 DLTs in first 6 patients	Enroll 3 additional patients and evaluate DLTs in this group of first 9 patients.
		≤5 DLTs in first 9 patients	Enroll full cohort of 15 patients.
		≥6 DLTs in first 9 patients	Proceed to Olara 15 mg/kg with Ifos Reduction Dose Level (new cohort of approximately 15 patients).
		≥9 DLTs in full 15 patients	Proceed to Olara 15 mg/kg with Ifos Reduction Dose Level (new cohort of approximately 15 patients).
		≤8 DLTs in full 15 patients	Proceed to Olara 20-mg/kg Loading Dose Cycle Dose Level.
Olara 15 mg/kg with Ifos Reduction	Olara 15 mg/kg D1, D8 Ifos 7.5 g/m² D1 to D3^a Dox 75 mg/m² D1 to D3	6 DLTs in first 6 patients	Halt study. No further patients enrolled.
		≤5 DLTs in first 6 patients	Enroll 3 additional patients and evaluate DLTs in this group of first 9 patients.
		≤5 DLTs in first 9 patients	Enroll full cohort of 15 patients.
		≥6 DLTs in first 9 patients	Halt study. No further patients enrolled.
		≥9 DLTs in full 15 patients	Halt study. No further patients enrolled.
		≤8 DLTs in full 15 patients	Proceed to Olara 20-mg/kg Loading Dose Cycle Dose Level with Ifos Reduction.
Olara 20-mg/kg Loading Dose Cycle	Olara 20 mg/kg D1, D8 of C1; then 15 mg/kg D1, D8 of C2 to C6 Ifos 10 g/m² D1 to D4^a Dox 75 mg/m² D1 to D3	6 DLTs in first 6 patients	Discontinue enrollment into cohort. Proceed to Recommended Dosing Regimen cohort with Olara 15 mg/kg as recommended dose.
		≤5 DLTs in first 6 patients	Enroll 3 additional patients and evaluate DLTs in this group of first 9 patients.
		≤5 DLTs in first 9 patients	Enroll full cohort of 15 patients.
		≥6 DLTs in first 9 patients	Discontinue enrollment into cohort. Proceed to Recommended Dosing Regimen cohort with Olara 15 mg/kg as recommended dose.
		≥9 DLTs in full 15 patients	Discontinue enrollment into cohort. Proceed to Recommended Dosing Regimen cohort with Olara 15 mg/kg as recommended dose.
		≤8 DLTs in full 15 patients	Proceed to Recommended Dosing Regimen cohort with Olara 20-mg/kg Loading Dose Cycle as recommended dose.

Dose Level	Regimen	If...	Then ^b ...
Olara 20-mg/kg Loading Dose Cycle with Ifos Reduction	Olara 20 mg/kg D1, D8 of C1; then 15 mg/kg D1, D8 of C2 to C6 Ifos 7.5 g/m ² D1 to D3 ^a Dox 75 mg/m ² D1 to D3	6 DLTs in first 6 patients	Discontinue enrollment into cohort. Proceed to Recommended Dosing Regimen cohort with Olara 15 mg/kg with Ifos reduction as recommended dose.
		≤5 DLTs in first 6 patients	Enroll 3 additional patients and evaluate DLTs in this group of first 9 patients.
		≤5 DLTs in first 9 patients	Enroll full cohort of 15 patients.
		≥6 DLTs in first 9 patients	Discontinue enrollment into cohort. Proceed to Recommended Dosing Regimen cohort with Olara 15 mg/kg and Ifos 7.5 g/m ² as recommended doses.
		≥9 DLTs in full 15 patients	Discontinue enrollment into cohort. Proceed to Recommended Dosing Regimen cohort with Olara 15 mg/kg and Ifos 7.5 g/m ² as recommended doses.
		≤8 DLTs in full 15 patients	Proceed to Recommended Dosing Regimen cohort with Olara 20 mg/kg Loading Dose Cycle and Ifos 7.5 g/m ² as recommended doses.
Recommended Dosing Regimen	Olara dose TBD Ifos dose TBD Dox 75 mg/m ² D1 to D3	Enroll 15 patients and treat with Recommended Dosing Regimen.	

Abbreviations: D = day; DLT = patients experiencing a dose-limiting toxicity; dox = doxorubicin; g = grams; Ifos = ifosfamide; kg = kilogram; m² = square meters; mg = milligrams; Olara = olaratumab; TBD = to be determined.

^a With concomitant mesna administration.

^b If a sufficient number of patients successfully complete the DLT period at a given dose level (ensuring the DLT threshold will not be exceeded), further enrollment may proceed as described in [Table JGDR.7](#), upon agreement of the Sponsor and Investigators.

7.3. Blinding

This is an open-label study.

7.4. Dosage Delays, Discontinuations and Modifications

To begin dosing at Cycle 2 and each Day 1 thereafter (for cycles in which olaratumab is administered with doxorubicin and ifosfamide), the following criteria must be fulfilled (see [Table JGDR.9](#) for hematological parameters for dosing olaratumab on Day 8):

- ANC $\geq 1.5 \times 10^3$ cells/ μ L (≥ 1500 cells/ μ L; $\geq 1.5 \times 10^9$ /L)
- Platelets $\geq 100 \times 10^3$ cells/ μ L ($\geq 100,000$ cells/ μ L; $\geq 100 \times 10^9$ cells/L)
- Hemoglobin ≥ 8.0 g/dL. Note: For study inclusion, hemoglobin ≥ 9.0 g/dL
- Total bilirubin below ULN. In patients with Gilbert's syndrome, total bilirubin should be <3 mg/dL
- Serum creatinine ≤ 1.5 times ULN. If creatinine is above ULN, the patient's creatinine clearance is ≥ 60 mL/min (refer to [Appendix 6](#) for the Cockcroft-Gault formula for creatinine clearance)
- AST and ALT $\leq 3 \times$ ULN, or $\leq 5 \times$ ULN if the transaminase elevation is due to liver metastases
- Nonhematologic toxicity must be Grade ≤ 2 or must have returned to baseline, unless the toxicity is deemed not clinically significant by the investigator or is a laboratory abnormality that is manageable by institutional standards (for example, low serum potassium, magnesium, or phosphate).

In addition, patients should be monitored for evidence of micro- and/or macroscopic hematuria and treated according to institutional standards.

7.4.1. Delays

In general, dose delays of 1 study drug (olaratumab, doxorubicin, or ifosfamide/mesna) due to toxicities outlined in [Section 7.4.3](#) will not necessitate delays of the other study drugs. However, close consideration must be made by the investigator to administer all study treatments per the schedule outlined in [Section 7.1](#).

Treatment may be delayed for up to 14 days to allow a patient sufficient time for recovery from study drug-related toxicity. If Day 8 treatment is delayed >7 days, treatment may be resumed with planned Day 1 treatment of the next cycle.

Dosing delay beyond 14 days may be permissible if AEs are not considered to be primarily related to olaratumab and the investigator deems continuation of study treatment to have clinical benefit for the patient. This decision has to be documented and be jointly made by the investigator and the Lilly team.

In the event of unforeseen circumstances or scheduling issues that require adjustments to the schedule, appropriate adjustments or delays to the schedule may be made following discussion between the investigator and the sponsor and written approval by the Lilly medical representative.

7.4.2. Discontinuations

The need to permanently discontinue doxorubicin and/or ifosfamide due to drug-related toxicity should be done according to local standard of care and labels. Criteria for olaratumab discontinuation are discussed in the olaratumab dose modification section (7.4.3.1) and in the olaratumab infusion-related reaction section (7.8.1).

Patients whose disease has not progressed at the time of doxorubicin, ifosfamide and mesna discontinuation will receive olaratumab as monotherapy until there is evidence of disease progression, death, intolerable toxicity, or other withdrawal criteria are met (Section 8). These patients will continue study assessments as outlined in [Table JGDR.2](#). Patients who undergo surgical tumor resection following study treatment are not eligible to receive olaratumab as monotherapy.

Patients who exhibit disease progression at the time of doxorubicin, ifosfamide and mesna discontinuation will receive post-treatment follow-up assessments as outlined in [Table JGDR.3](#).

7.4.3. Dose Modifications

General guidelines for dose modifications are provided below. Sections 7.4.3.2 and 7.4.3.3 outline guidelines for dose modifications of doxorubicin and ifosfamide, respectively; variations from these guidelines may be allowed according to local standard of care and labels.

7.4.3.1. Olaratumab Dose Modifications

A reduction in the dose of olaratumab will be permitted if the doses of doxorubicin and ifosfamide have been previously reduced for toxicity, and the same or similar toxicity has recurred despite reduction of doxorubicin, ifosfamide and mesna, and the toxicity is deemed potentially related to the addition of olaratumab in combination with doxorubicin, ifosfamide and mesna. In this scenario, an olaratumab dose reduction should occur in conjunction with a reduction in the doxorubicin and ifosfamide doses according to the guidance outlined in Sections 7.4.3.1.1 and 7.4.3.1.2.

A second reduction in the olaratumab dose will not be permitted during treatment with combination therapy of olaratumab plus doxorubicin and ifosfamide.

Patients who have not progressed on study will receive olaratumab as monotherapy following discontinuation of the combination therapy until there is evidence of disease progression, death, intolerable toxicity, or other withdrawal criteria are met. Patients receiving olaratumab as monotherapy will have assessments performed as per [Table JGDR.2](#)

Patients who have a dose reduction of olaratumab during the combination therapy portion and then proceeding to receive olaratumab monotherapy after discontinuation of doxorubicin and ifosfamide combination may have their dose of olaratumab re-escalated to the original dose level at the investigator's discretion.

7.4.3.1.1. *Hematologic Toxicity*

Table JGDR.8 shows olaratumab dose modifications that should be made for hematologic toxicities judged as potentially related to olaratumab in combination with doxorubicin, ifosfamide and mesna, and that have recurred or failed to improve/resolve despite 1 reduction in doxorubicin and ifosfamide doses. These guidelines should be used for olaratumab dosing, when given in combination with doxorubicin and ifosfamide.

Table JGDR.8. General Guidelines for Olaratumab Dose Modification due to Hematologic Toxicities

Toxicity	Dose Modification
Neutropenia	
ANC Grades 1-3	No dose modification required
ANC <500 cells/ μ L (Grade \geq 4)	No treatment administered; treatment cycle delayed
At re-treatment: If \geq Grade 3 neutropenic fever/infection has occurred and 1 reduction in doxorubicin, ifosfamide and mesna doses has already occurred	Withhold dose until ANC is \geq 1500 cells/ μ L; 
 • 15-mg/kg Dose Level: Reduce dose to 12 mg/kg • 20-mg/kg Loading Dose Cycle Level: Reduce dose to 15 mg/kg
If Grade 4 neutropenia lasting \geq 1 week has occurred and 1 reduction in doxorubicin, ifosfamide and mesna doses has already occurred	Withhold dose until ANC is \geq 1500 cells/ μ L; 
 • 15-mg/kg Dose Level: Reduce dose to 12 mg/kg • 20-mg/kg Loading Dose Cycle Level: Reduce dose to 15 mg/kg
Grade 4 ANC without fever/infection lasting \leq 1 week	Administer next olaratumab at full dose, at investigator's discretion
After 1 reduction of olaratumab and 2 reductions of doxorubicin, ifosfamide and mesna, recurrence of either: 1) \geq Grade 3 neutropenic fever/infection 2) Grade 4 neutropenia lasting \geq 1 week	Discontinue combination therapy (olaratumab + doxorubicin/ifosfamide/mesna). Patients who have not progressed will receive olaratumab as monotherapy until there is evidence of disease progression, death, intolerable toxicity, or other withdrawal criteria are met.

Abbreviation: ANC = absolute neutrophil count.

Omitting the Day 8 dose of olaratumab based on ANC and platelet counts judged as potentially related to olaratumab in combination with doxorubicin, ifosfamide, and mesna is permissible as shown in Table JGDR.9.

Table JGDR.9. Olaratumab Day 8 Dosing Algorithm Based on ANC and Platelet Count

Treatment Day	ANC (cells/ μ L)		Platelet Count (cells/ μ L)	Olaratumab
Day 8	≥ 500	and	$\geq 75,000$	Administer
	< 500	and	Any	Omit ^a
	Any	and	$< 75,000$	Omit

Abbreviations: ANC = absolute neutrophil count; μ L = microliter.

^a Day 8 administration of olaratumab may be delayed for a maximum of 7 days. If the ANC level has not increased to ≥ 500 cells/ μ L within 7 days, then the Day 8 olaratumab dose in that cycle should be skipped and dosing resumed on Day 1 of the following cycle (if criteria for dosing are met). If all dosing criteria are met, a delay or omission of the Day 8 olaratumab dose should not result in a delay of the Day 1 olaratumab dose of the following cycle.

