5.1.1. Dose-Finding Phase: Olaratumab 15-mg/kg Dose Level

The purpose of this single-arm cohort is to determine whether a 15-mg/kg dose of olaratumab (on Days 1 and 8) may be safely added to the doxorubicin, ifosfamide and mesna regimen in patients with advanced or metastatic STS. No intrapatient dose escalation is permitted in this cohort. Patients who do not complete Cycle 1 treatment for reasons other than a DLT will be replaced. Safety data for this patient cohort will be reviewed prior to dose escalation. The total number of patients with DLTs and the type of DLTs will be considered prior to making a decision to escalate the olaratumab dose.

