5.1.2. Dose-Finding Phase: Olaratumab 20 mg/kg Loading Dose Cycle Level

The purpose of this single arm cohort is to determine whether a 20 mg/kg loading dose cycle of olaratumab (given on Days 1 and 8 of Cycle 1 only, followed by 15 mg/kg on Days 1 and 8 of subsequent cycles) may be safely added to the doxorubicin, ifosfamide and mesna regimen in patients with advanced or metastatic STS. Patients who do not complete Cycle 1 treatment for reasons other than a DLT will be replaced. Safety data for this will be reviewed prior to dose determination for the Dose Confirmation Phase. The total number of patients with DLTs and the type of DLTs will be considered prior to making a dose determination.

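### The olaratumab reduction step for Loading Dose patients reduces nothing: they are already scheduled for 15 mg/kg by the time it can apply

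*Protocol*

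**What the plan says.** Protocol Section 5.1.2 defines the Loading Dose regimen as 20 mg/kg "given on Days 1 and 8 of Cycle 1 only, followed by 15 mg/kg on Days 1 and 8 of subsequent cycles". Table JGDR.7 repeats it: "Olara 20 mg/kg D1, D8 of C1; then 15 mg/kg D1, D8 of C2 to C6".

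Section 7.4.3.1 permits an olaratumab reduction only when doxorubicin and ifosfamide have been reduced for toxicity and "the same or similar toxicity has recurred despite reduction of doxorubicin, ifosfamide and mesna". Two rows of Table JGDR.8 (neutropenic fever or infection, and prolonged Grade 4 neutropenia) and two rows of Table JGDR.10 (Grade 3 and Grade 4 nonhematologic toxicity) lower the olaratumab dose. Each carries the condition that "1 reduction in doxorubicin, ifosfamide and mesna doses has already occurred". Each sends the 15-mg/kg cohort to 12 mg/kg and gives the other cohort "20-mg/kg Loading Dose Cycle Level: Reduce dose to 15 mg/kg".

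Section 7.4.3.1 rules out a second olaratumab reduction during combination therapy. The last row of Table JGDR.8 ends combination therapy for an event that comes "After 1 reduction of olaratumab and 2 reductions of doxorubicin, ifosfamide and mesna, recurrence of either" of two neutropenic events, so the protocol expects the olaratumab step to have been used by then.

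**The concern.** The Loading Dose line names as its reduced dose the dose the patient is already scheduled to receive whenever the rule can apply. Two patients, both scheduled for 15 mg/kg and both with the same recurrent toxicity judged potentially related to adding olaratumab, are then handled differently: one is cut and the other is not.

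The sequence that follows is also unclear. A site cannot tell whether a step from 15 to 15 mg/kg uses up the one permitted reduction, or whether it counts as the olaratumab reduction in the stopping row of Table JGDR.8.

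The affected group is not confined to one dose-finding cohort. The loading regimen may also be given with reduced ifosfamide, and it becomes the Dose Confirmation regimen if 8 or fewer of 15 patients have DLTs.

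**Working it through.** No power or sample-size figure lies behind this point. The figure to check is the stated reduced dose of 15 mg/kg, set against the schedule and the conditions for using it.

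**1. When the rule can apply.** Doxorubicin is given on Days 1 to 3 and ifosfamide on Days 1 to 4. Table JGDR.11 lowers doxorubicin at re-treatment. Table JGDR.12 lowers ifosfamide according to the worst toxicity of the previous cycle. The first chemotherapy reduction therefore falls in Cycle 2 at the earliest, and the toxicity must then recur. Because the olaratumab reduction is to accompany a further chemotherapy reduction (Section 7.4.3.1), the earliest ordinary point is Cycle 3 Day 1. A mid-cycle change in Cycle 1 is not strictly excluded, hence the qualifier that this holds in practice.

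**2. Size per dose.** Reduction = (scheduled − reduced) / scheduled.

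- Loading Dose, Cycle 1: (20 − 15)/20 = 25%, but the conditions cannot in practice be met.
- Loading Dose, Cycles 2 to 6: (15 − 15)/15 = 0%.
- 15-mg/kg cohort, any cycle: (15 − 12)/15 = 20%.

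With two doses per cycle, this is 2 × 15 = 30 mg/kg against 2 × 12 = 24 mg/kg.

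**3. Size over the remaining combination cycles**, if every dose through Cycle 6 is given:

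| Step taken at | Doses left | At 15 mg/kg | At 12 mg/kg | Difference |
|---|---|---|---|---|
| Cycle 3 Day 1 | 8 | 120 | 96 | 24 |
| Cycle 4 Day 1 | 6 | 90 | 72 | 18 |
| Cycle 5 Day 1 | 4 | 60 | 48 | 12 |
| Cycle 6 Day 1 | 2 | 30 | 24 | 6 |

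Day 8 omissions or early discontinuation make the difference smaller. It is zero if combination therapy stops first.

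**4. How often the row is reached.** Under the default chemotherapy tables, seldom:

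- *Febrile neutropenia alone.* Episode 1: doxorubicin 75 to about 60 mg/m², ifosfamide unchanged at 10 g/m², so the condition is not met. Episode 2: doxorubicin to 45 mg/m², ifosfamide 10 × 0.8 = 8 g/m², and the condition was not met beforehand. Episode 3: combination therapy stops.
- *Prolonged Grade 4 neutropenia.* Table JGDR.12 has no ifosfamide row for it.
- *Nonhematologic toxicity.* Ifosfamide is cut for Grade 3, but Section 7.4.3.2.2 cuts doxorubicin only for Grade 4, and related Grade 4 toxicity already stops combination therapy in Table JGDR.12.

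The row can still be reached when toxicities coincide. Suppose Cycle 1 brings neutropenic fever (doxorubicin to about 60 mg/m²) together with platelets below 75,000/mm³ for more than a week (ifosfamide to 8 g/m²), and Cycle 2 brings neutropenic fever again. The condition is then met at Cycle 3 Day 1. It can also be met where chemotherapy is adjusted to local practice, which Sections 7.4.3, 7.4.3.2 and 7.4.3.3 allow.

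**The case against.** **The labels could mean the dose being received.** Section 7.4.3.1 speaks of re-escalation to a patient's original dose level, so dose level is not always a cohort name. On that reading a Loading Dose patient in Cycle 2 or later would follow the 15-mg/kg line down to 12 mg/kg. But the 20-mg/kg line would then in practice never apply. The row labels also track the headings of Sections 5.1.1 and 5.1.2, "Dose-Finding Phase: Olaratumab 15-mg/kg Dose Level" and "Dose-Finding Phase: Olaratumab 20 mg/kg Loading Dose Cycle Level". The cohort reading is the more natural one, and the line fails on either.

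**These are guidelines, and the reduction is only permitted.** Both table titles do describe general guidelines. Yet the accompanying text says the modifications should be made, Table JGDR.10 heads its column as required, and the allowance for local variation in Section 7.4.3 names only the doxorubicin and ifosfamide sections.

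**Recurrence is not the only trigger.** The text before Table JGDR.8 also admits toxicity that failed to improve or resolve. This stands, but a prior chemotherapy reduction is still needed, so the timing does not change.

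**The 24 mg/kg is not a strict maximum.** If nonhematologic dosing resumed at Cycle 2 Day 8, nine doses would differ by 9 × 3 = 27 mg/kg. The requirement to reduce chemotherapy at the same time favours Cycle 3 Day 1.

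**Few patients reach the row, and they remain protected.** This stands and sets the weight of the point. Dosing is withheld until recovery, chemotherapy is reduced further, resuming after Grade 4 nonhematologic toxicity requires consulting the sponsor's physician, and further recurrence stops combination therapy.

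**A reduction to 12 mg/kg is the sponsor's clinical choice.** Section 5.5.1 justifies loading by avoiding subtherapeutic levels. It explains the higher Cycle 1 dose but gives no reason for a 15 mg/kg floor in later cycles.

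**Conclusion.** The concern holds. It is an internal inconsistency in a safety rule rather than a miscalculation. As written, the Loading Dose line gives a 0% olaratumab reduction where the 15-mg/kg cohort receives 20%, with a cumulative difference of at most 24 mg/kg through Cycle 6.

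This rests on reading the row labels as cohort names, on chemotherapy reductions taking effect from the next cycle, and on all remaining doses being given. How many patients would reach the row cannot be derived from the documents.

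The text should be corrected, but the reach is limited. DLT thresholds, sample size and analyses are unaffected.

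**What to change.** In both tables, state that Loading Dose patients receiving 15 mg/kg (Cycle 2 onward) reduce to 12 mg/kg, and add one sentence saying that this is the single olaratumab reduction permitted during combination therapy. The 12 mg/kg is taken from the 15-mg/kg cohort's line; the documents give no separate value for Loading Dose patients. If the sponsor intends no reduction for them, the tables should say so, and say how the stopping row of Table JGDR.8 then applies.

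The cost is wording in a protocol amendment: the Loading Dose line in four places (two rows in each table) and the clarifying sentence.

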7.4.3.3. Ifosfamide Toxicities and Dose Modifications

Dose modifications of ifosfamide will follow the guidelines outlined below and may be adjusted according to local standard of care and label. Two reductions in ifosfamide dose for toxicity will be permitted during the study. If a third dose reduction is necessary, the patient will be discontinued from the combination therapy (olaratumab + doxorubicin/ifosfamide/mesna) and followed as outlined in Section 7.4.2.

General guidelines for ifosfamide dose modification are shown in Table JGDR.12. Dose modifications of ifosfamide due to hepatic impairment are shown in Table JGDR.13.

Table JGDR.12. General Guidelines for Dose Modification of Ifosfamide due to Toxicity

Worst Toxicity/Counts in Previous Cycle	Ifosfamide Dose Reduction ^a
Febrile neutropenia	First episode: Maintain full dose Subsequent episodes: Decrease 20%
Platelets <75,000/mm ³	If less than 1 week duration: Maintain full dose If greater than 1 week duration: Decrease 20%
Thrombocytopenic bleeding	Decrease 20%
Somnolence or other signs of encephalopathy	Discontinue combination therapy (olaratumab + doxorubicin/ifosfamide/mesna) and follow per Section 7.4.2. Administer methylene blue 50 mg intravenously every 4 hours until resolution.
Grade 3 or 4 neurotoxicity other than encephalopathy	Discontinue combination therapy (olaratumab + doxorubicin/ifosfamide/mesna) and follow per Section 7.4.2.
Grade 3 related organ toxicity/nonhematologic	Decrease 20%
Grade 4 related organ toxicity/nonhematologic	Discontinue combination therapy (olaratumab + doxorubicin/ifosfamide/mesna) and follow per Section 7.4.2.

Abbreviation: mg = milligrams.

^a Do not re-treat until criteria in Section 7.4 are met.

Table JGDR.13. Dose Modification of Ifosfamide due to Hepatic Impairment

Bilirubin	and/or	AST/ALT	Ifosfamide Dose Reduction ^a
1-2 × ULN		<2 × ULN	Full dose
2-4 × ULN		2-5 × ULN	75% of initial dose
>4 × ULN		>5 ULN	Discontinue combination therapy (olaratumab + doxorubicin/ifosfamide/mesna) and follow per Section 7.4.2.

Abbreviations: ALT = alanine aminotransferase; AST = aspartate aminotransferase; ULN = upper limit of normal.

^a Based on clinical judgment – less conservative adjustments can be considered if hepatic changes are secondary to metastases rather than hepatic cirrhosis or hepatitis.

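### At the loading-dose level the olaratumab reduction to 15 mg/kg equals the dose already scheduled, so patients in that cohort have no effective reduction step

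*Protocol*

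**What the plan says.** **Loading-dose schedule.** Protocol Table JGDR.7 gives the regimen as "Olara 20 mg/kg D1, D8 of C1; then 15 mg/kg D1, D8 of C2 to C6".

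**When olaratumab may be reduced.** Section 7.4.3.1 states: "A reduction in the dose of olaratumab will be permitted if the doses of doxorubicin and ifosfamide have been previously reduced for toxicity". The same or a similar toxicity must also have recurred and be judged potentially related to adding olaratumab. The reduction rows of Tables JGDR.8 and JGDR.10 repeat the condition that "1 reduction in doxorubicin, ifosfamide and mesna doses has already occurred". Only one olaratumab reduction is allowed during combination therapy.

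**Size of the reduction.** At the 15 mg/kg level olaratumab goes to 12 mg/kg. At the loading-dose level the line reads "20-mg/kg Loading Dose Cycle Level: Reduce dose to 15 mg/kg". It stands in four rows: two in Table JGDR.8 (neutropenic fever or infection; prolonged Grade 4 neutropenia) and two in Table JGDR.10 (Grade 3; Grade 4).

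**When chemotherapy is reduced.** Table JGDR.11 lowers doxorubicin at re-treatment. Table JGDR.12 lowers ifosfamide according to "Worst Toxicity/Counts in Previous Cycle". Section 7.4.3 allows local variation from the doxorubicin and ifosfamide guidance (7.4.3.2 and 7.4.3.3). It does not extend this to the olaratumab rules in 7.4.3.1.

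**The concern.** A reduction rule should lower a dose when it is triggered. At the loading-dose level the target equals the scheduled maintenance dose. The trigger needs a chemotherapy reduction followed by a recurrence, and by then the 20 mg/kg infusions are over.

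A site that follows the table would withhold olaratumab and then resume it at the same 15 mg/kg, although the event was severe, had recurred and was judged potentially related to adding olaratumab. A patient with the same history at the 15 mg/kg level would resume at 12 mg/kg. The loading dose may become the recommended regimen, on which the protocol aims to treat about 30 patients. The study's primary objective is safety and the choice of dosing regimen. SAP section 5.8.1 also summarises dose reductions and dose intensity, and a nominal reduction from 15 to 15 mg/kg would make those summaries hard to read.

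**Working it through.** The plan states no figure here to reproduce. The check compares the timing of the trigger with the scheduled dose.

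**Step 1. Latest 20 mg/kg infusion.** Olaratumab is due on Days 1 and 8 of Cycle 1. Table JGDR.9, footnote a, says "Day 8 administration of olaratumab may be delayed for a maximum of 7 days"; after that the dose is skipped. Latest day: 8 + 7 = Day 15.

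**Step 2. Earliest default chemotherapy reduction.** Doxorubicin is given on Days 1 to 3 and ifosfamide on Days 1 to 4. Reductions follow at re-treatment or on the previous cycle's toxicity, so the earliest is Cycle 2 Day 1. That is Day 22, or 22 − 3 = Day 19 with the 3-day cycle window in Table JGDR.6. Both fall after Day 15.

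**Step 3. Earliest olaratumab reduction.** The toxicity must recur after that chemotherapy reduction. The first infusion that could be affected is therefore in Cycle 2 at the earliest.

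**Step 4. Scheduled against reduced dose.**

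| Level | Cycle | Scheduled (mg/kg) | Reduced to (mg/kg) | Change |
|---|---|---|---|---|
| 15 mg/kg | 2 to 6 | 15 | 12 | (12 − 15)/15 = −20% |
| Loading dose | 1 (not reachable by default) | 20 | 15 | (15 − 20)/20 = −25% |
| Loading dose | 2 to 6 | 15 | 15 | (15 − 15)/15 = 0% |

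Over Cycles 2 to 6 there are 5 × 2 = 10 infusions at the loading-dose level. The most the rule can remove is 10 × (15 − 15) = 0 mg/kg.

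**Step 5. The exception.** Under local practice both drugs could be lowered on the remaining chemotherapy days of Cycle 1. If the toxicity then recurred before the Day 8 olaratumab dose, a cut from 20 to 15 mg/kg would be real. No default rule in the protocol produces this sequence.

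**Step 6. Fit with Tables JGDR.11 and JGDR.12 in repeated febrile neutropenia.** This assumes no other cause for a reduction. Table JGDR.11 takes doxorubicin to about 60 mg/m², then 45 mg/m², then stops the combination. Table JGDR.12 leaves ifosfamide unchanged after the first episode and takes off 20% after later ones.

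| Event | Earlier reductions (dox, ifos) | Table JGDR.8 if both drugs must have been reduced | Table JGDR.8 if doxorubicin alone counts | Table JGDR.11 |
|---|---|---|---|---|
| 1 | 0, 0 | no reduction | no reduction | about 60 mg/m² |
| 2 | 1, 0 | no reduction | reduce olaratumab | 45 mg/m² |
| 3 | 2, 1 | reduce olaratumab | stop | stop |

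Tables JGDR.8 and JGDR.11 differ at the third event only when the condition is read drug by drug.

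**The case against.** **Other protections apply.** Olaratumab is withheld until the ANC is at least 1500 cells/µL or, for nonhematologic toxicity, until Grade 1 or baseline. Day 8 doses can be omitted on low counts, G-CSF is mandatory, chemotherapy is reduced, and the investigator may stop treatment. All of this stands and limits the harm, but none of it supplies a lower olaratumab dose.

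**The tables are general guidelines.** Their titles say so. However, Table JGDR.10 heads its column as required modifications, and the local-variation clause does not cover olaratumab.

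**Chemotherapy is meant to be reduced before olaratumab.** That order is deliberate and reasonable. It does not explain why one cohort then gets a 20% step and the other none.

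**Stronger readings the documents do not support.** A reader might infer that the whole olaratumab reduction scheme fails. It does not: the 15 mg/kg line works. A reader might also infer that Tables JGDR.8 and JGDR.11 contradict each other at a third neutropenic event with nothing to settle it. Section 7.4.3.1.1 confines Table JGDR.8 to olaratumab given with doxorubicin and ifosfamide, so a stop of the combination naturally governs. Section 7.4.3.1 points the same way, since "an olaratumab dose reduction should occur in conjunction with a reduction in the doxorubicin and ifosfamide doses" and Table JGDR.11 has no doxorubicin step below 45 mg/m². Finally, the lack of an olaratumab reduction at a second neutropenic event is not shown to be an error. It depends on how the condition is read, and that is the sponsor's choice.

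**Conclusion.** The loading-dose instruction in Tables JGDR.8 and JGDR.10 is wrong as written. By default it lowers no dose: 0% per infusion, against 20% at the 15 mg/kg level. If it counts as the one permitted reduction, the bar on a second closes off anything lower during combination therapy. If it does not count, the tables still name no lower dose.

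This rests on the protocol's default timing of chemotherapy reductions; the only exception is the Cycle 1 sequence in step 5. It holds for hematologic and nonhematologic toxicity alike and does not depend on how the chemotherapy condition is read.

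The fit between Tables JGDR.8, JGDR.11 and JGDR.12 needs clarification only. The documents give no rate of recurrent toxicity, so the number of patients who would reach the line cannot be derived and none is offered. A reader might fear for the dose-finding decisions, but DLT rules, cohort thresholds and sample size are unaffected. The correction should be made because it concerns dosing after repeated severe toxicity and is cheap.

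**What to change.** **Main change.** In the four rows of Tables JGDR.8 and JGDR.10, set the loading-dose reduction after Cycle 1 to 12 mg/kg, as at the 15 mg/kg level.

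**Clarifications in the same edit.** State that the third-incidence stop in Table JGDR.11 takes precedence over the reduction rows of Table JGDR.8. State whether a doxorubicin reduction alone satisfies the Table JGDR.8 condition or ifosfamide must also have been reduced.

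**Cost.** One short protocol amendment to section 7.4.3.1 and its tables. Visits, DLT thresholds, cohort sizes and the planned analyses stay as they are.
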